as the sole drug therapy for hyponatremia ('urea-only' patients). Overall, 58 patients received urea (7.5-90 g/day) over a median of 4.5 days and demonstrated an increase in PNa from 124 to 131 mmol/L (p<0.001). Among 12 'urea-only' treated patients, PNa increased from 125 to 131 mmol/L (p=0.001) with a larger increase in PNa by 24 h (2.5 mmol/L [IQR 0-4.5] vs. -0.5 mmol/L [IQR -2.5 to 1.5], p=0.04) and more patients normalized PNa (33% vs. 8%, p=0.08) compared to a control group. No patients experienced overly rapid correction of PNa and no serious adverse events were reported. While our study was retrospective and limited to hospitalized patients, the findings support the potential efficacy and safety of this agent. After the publication of our study, two other observational studies were published supporting the efficacy, safety, and tolerability of oral urea in hyponatremia.(28, 29) Just one past study compared urea to other therapies for hyponatremia. Soupart et al. compared urea to vasopressin antagonists in 13 patients with chronic SIADH.(30) Patients were treated with vaptans (satavaptan and tolvaptan) for 1 year, during which PNa increased from 125±3 mmol/L to 135±3 mmol/L. Vaptans were then discontinued, leading to recurrent hyponatremia. After an 8-day washout period, oral urea was prescribed for 1 year with normalization of PNa in all patients (mean PNa 135±2 mmol/L). Patients tolerated urea well with no significant side effects. To date, there have been no studies comparing urea to fluid restriction.

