#### Intervention (oral urea) and study period 1:

Patients randomized to study group "Urea ON, then Urea OFF" (N=15) will begin 42 ± 3 days of urea therapy, while those randomized to study group "Urea OFF, then Urea ON" (N=15) will not receive urea during this period. All patients will be asked to restrict their fluid intake to  $\leq$ 1.2 L/day during period 1. We will provide participants with a protocol for recording their daily fluid intake which includes carefully measuring all ingested fluids with a measuring cup and recording them on a study diary during the entire study period. We will use the new American formulation of oral urea (i.e., Ure-NaTM), which is packaged as a powder that is mixed with 4 oz. of water for oral consumption. Group "Urea ON, then Urea OFF" patients will be given 48 powder pouches of Ure-Na (15 g of urea per pouch) and will be instructed to start at a dose of 15 g once daily. Dose titration will be based on the absolute increase in PNa on days 7 ± 2 and 14 ± 2 as follows:

- Day 7: If PNa increases ≥3 mmol/L from baseline, then continue same urea dose. If PNa increases <3 mmol/L from baseline, then increase urea to next dose.
- Day 14: If PNa increases ≥ 6 mmol/L from baseline, or PNa increases <6 mmol/L from baseline and PNa ≥135 mmol/ L, then continue same urea dose. If PNa increases <6 mmol/L from baseline and PNa <135 mmo/L, then increase urea to next dose.

The dosing scheme for urea will involve increasing when appropriate, from the starting dose of 15 g/day, to 30 g/day in 2 divided doses, and subsequently, when appropriate, from 30 g/day to 60 g/day (in 2 divided doses). The maximal dose of urea administered will be 60 g/day. Patients will undergo a PNa check approximately  $7 \pm 2$  days after a urea dose adjustment to less than the maximal dose of urea allowed. Patients will record the doses of urea they consume each day during treatment period 1 in the study diary.

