#### Follow-up research assessments:

All patients in group "Urea ON, then Urea OFF" will have scheduled follow up assessments on days 7, 14, and 42 as follows:

- Day 7: Phone interview and basic metabolic panel (BMP).
- Day 14: Phone interview and BMP. More boxes of Ure-Na will be mailed if needed to complete the study.
- Day 42: same assessment as in the baseline study visit

The phone interviews visits will focus on assessing side effects, tolerability, and adherence to urea and as appropriate, dose titration of urea. Side effects and tolerability will be assessed with questionnaires (See Medication Side Effects Questionnaire and Medication Acceptability Questionnaire). Patient also will be asked to bring their study diary to the in-person clinic visits to track their adherence to fluid restriction and urea. Visits at day 0 and day 42 will take place in the Neuromuscular Research Laboratory at the University of Pittsburgh. BMP assessment on days 7, 14 will take place at the UPMC clinical laboratory of patient's choice. At the 42-day visit, patients will be asked to return their study diary and any urea doses they did not consume. During period 1 of the study, patients randomized to group "Urea OFF, then Urea ON" will undergo same assessments as outlined for group "Urea ON, then Urea OFF", although they will not be asked about tolerability or adherence to urea as they will not be on this treatment during this period.

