- The research coordinator will call the patient on the phone to ask some questions about any new symptoms patient might have experienced since his/her last visit.
- The research coordinator will direct the patient to go the UPMC clinical laboratory of the patient's choice that day to have his blood drawn for analysis of a basic metabolic panel.
- The research coordinator will instruct the patient to bring his fluid and urea intake diaries to the next study visit.
- The research coordinator will give or mail the patient a container with instructions to collect urine for 24 hours prior to next study visit.
- If patient is taking urea then research coordinator will give and/or mail the patient enough urea powder pouches to complete his/her participation in this period of the study.
- If patient is taking urea, we might call the participant on the phone to ask to change the dose of urea depending on the sodium level results.
- If urea dose is adjusted to less than the maximum allowed dose, research coordinator will direct the patient to go the UPMC clinical laboratory of the patient's choice in approximately 7 days to have his/her blood drawn for analysis of a basic metabolic panel.
- This visit will last approximately 30 minutes.

Reminder telephone call

• The research coordinator will call the patient on the phone 48-72 hours before the next study visit to remind him/her of the upcoming study visit.

Fourth study visit (Day 42 of Period 1)

- Patient will come in person to the University of Pittsburgh Neuromuscular Research Laboratory located at [name].
- The research coordinator will collect the patient's fluid and urea intake diaries.
- The research coordinator will ask the patient some questions about any new symptoms patient might have experienced since his/her last visit.
- If patient is taking urea then the research coordinator will ask patient some questions related to acceptability of urea.
- Patient will bring the container with the 24-hour urine collection he/she started the day prior. The research coordinator will send the specimen promptly to the UPMC Presbyterian clinical laboratory for processing and analysis of the following: creatinine, urea nitrogen, uric acid, osmolality, sodium, and potassium

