- The research coordinator will draw approximately 14 mL of patient's blood and send the specimen promptly to the UPMC Presbyterian clinical laboratory for processing and analysis of the following: basic metabolic panel, plasma osmolality, and plasma uric acid.
- Patient will complete the SF-12 survey with pen and paper.
- A co-investigator will test patients' reactions and decision making using specialized software on a tablet computer.
- A co-investigator will test patients' balance while standing on a specialized piece of equipment. Patient will be asked to stand on both legs on top of a platform in a dynamic moving environment. Patient will go through six conditions, with three trials per condition, lasting about 20 seconds each. Patient will be asked to look forward, and stand as motionless as possible with your arms at your sides. The six conditions

include the possibility of moving surroundings or moving base of support. If patient move or lose his/her balance during the procedures, patient will be asked to repeat that part again. Patient will be supported by means of a harness in the equipment to make sure he/she cannot fall over while performing the tests.

- The research coordinator will ask patient to stop fluid restriction.
- If patient is taking urea then the research coordinator will instruct the patient to stop taking urea and return all the urea pouches he/she did not use to the research coordinator.
- The research coordinator will provide the patient with a container with instructions to collect urine for 24 hours prior to next study visit.
- This visit will last approximately 2.5 hours.

Reminder telephone call

• The research coordinator will call the patient on the phone 48-72 hours before the next study visit to remind him/her of the upcoming study visit.

Fifth study visit (Day 0 of Period 2)

- Patient will come in person to the University of Pittsburgh Neuromuscular Research Laboratory located at [name].
- Patient will bring the container with the 24-hour urine collection he/she started the day prior. The research coordinator will send the specimen promptly to the UPMC Presbyterian clinical laboratory for processing and analysis of the following: creatinine, urea nitrogen, uric acid, osmolality, sodium, and potassium.

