Our study propose to use the oral route for urea administration. Pharmacological urea currently exist in topical and oral formulations. The oral formulation allows for systemic absorption and renal excretion causing the desired pharmacological effect (i.e. osmotic diuresis). The initial dose of urea to be administered during our study will be 15 g/day but this can be titrated in subsequent study visits based on efficacy and safety. The next dose in our titration algorithm is 30 g/day (in 2 divided doses), and the next and maximal dose allowed will be 60 g day (in 2 divided doses). The European Clinical practice guideline on diagnosis and treatment of hyponatraemia(26) recommended a urea dose of 0.25 - 0.5 g/kg/day which for a 60 kg person constitutes between 15 and 30 g of urea per day. Our study using Ure-Na™ at the University of Pittsburgh Medical Center(4) showed that patients were treated with doses ranging from 7.5 g/day up to 90 g/day. however most patients required doses between 15 and 30 g. The rationale behind the divided doses with doses of 30 or 60 g/day of urea is double. Urea's half-life is 2.5 h and a single dose of urea is completely eliminated via the kidneys within 12 h. Also, higher doses of urea are more likely to cause gastrointestinal side effects. Therefore, to achieve a sustained effect while minimizing adverse reactions a twice daily dose of urea will be more appropriate. While past observational studies demonstrated a potential benefit of increasing plasma sodium on neurocognitive outcomes within 1 week (8, 32, 33), we have increased the treatment duration to 42 ± 3 days to ensure a longer period of plasma sodium normalization that captures the potential beneficial effects of urea on these outcomes.

For a summary of the information related to the human pharmacokinetics and human safety profile of urea, as well as findings from non-clinical studies that support the evaluation of urea in humans, please, refer to: *Toxicological Review of Urea by the United Stated Environmental Protection Agency (EPA).* 

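### The step from 30 to 60 g/day of urea at day 14 is the only dose increase with no sodium check about a week later; the first panel at 60 g/day is at day 42, when urea is stopped

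*Combined protocol and SAP*

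**What the plan says.** Urea starts at 15 g/day and can go up one level at day 7 and one level at day 14, from 15 to 30 to 60 g/day (Section 2.2, Intervention and study period 1; Section 2.3). Period 2 uses the same titration.

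A further sodium check is due about 7 ± 2 "days after a urea dose adjustment to less than the maximal dose of urea allowed". The day-14 visit descriptions under Research activities repeat the limit for both periods: "If urea dose is adjusted to less than the maximum allowed dose, research coordinator will direct the patient" to a local laboratory for a basic metabolic panel in about 7 days.

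Otherwise patients "will have scheduled follow up assessments on days 7, 14, and 42 as follows", and Table 1 shows basic metabolic panels at days 0, 7, 14 and 42 only. At day 14 the patient receives "enough urea powder pouches to complete his/her participation in this period of the study". The only later contact listed is a reminder call 48 to 72 hours before the next visit. At the day-42 visit the panel is drawn and dosing ends: "If patient is taking urea then the research coordinator will instruct the patient to stop taking urea and return all the urea pouches".

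On the dose itself, Section 2.3.3 reports that a European guideline "recommended a urea dose of 0.25 - 0.5 g/kg/day which for a 60 kg person constitutes between 15 and 30 g" per day. It says of the group's own earlier patients, who received up to 90 g/day, "however most patients required doses between 15 and 30 g". Section 1.3 describes those patients as hospitalized: "Overall, 58 patients received urea (7.5-90 g/day) over a median of 4.5 days".

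**The concern.** The increase left without a check is the largest one (30 g, against 15 g for the other step), and it leads to the dose with the least support in the protocol. In Section 2.3.3's own 60-kg example, 60 g is 1.0 g/kg/day, twice the upper end of the cited range. Here it would be taken for about four weeks by outpatients asked to hold fluids to 1.2 L/day or less, with eGFR allowed down to 45 (Section 3.2).

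The limit fits a titration purpose, because no further increase exists at 60 g/day. But the protocol also uses sodium checks for safety. Section 2.3.6 allows withdrawal when missed checks make it unwise to continue urea, and Sections 2.3.2 and 2.3.3 let sodium, side effects and safety change the dose. Section 9.4 has the investigator review safety data as they are generated, but between days 14 and 42 no laboratory result at 60 g/day is scheduled. A change in sodium or kidney function without symptoms would first be seen on the last day of treatment, too late to act on.

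**Working it through.** **1. Time from each possible increase to the next panel.** Inputs: titration at days 7 ± 2 and 14 ± 2; panels at days 7, 14 and 42 ± 3; an extra check about 7 days after a change to a dose below 60 g/day.

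| Increase | Next panel | Gap |
|---|---|---|
| Day 7, 15 to 30 g | day 14 | 7 days |
| Day 14, 15 to 30 g | about day 21 (extra check) | 7 days |
| Day 14, 30 to 60 g | day 42 | 42 − 14 = 28 days |

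With visit windows, the last gap runs from (42 − 3) − (14 + 2) = 23 to (42 + 3) − (14 − 2) = 33 days. It is 28/42, or two thirds, of the treatment period. The titration rule cannot bring anyone to 60 g/day before day 14, so day 42 is the first scheduled panel at that dose. Patients whose dose is unchanged at day 14 also wait until day 42, but they have already had a panel on that dose.

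**2. Supply.** A patient raised at both visits uses 7 × 1 + 7 × 2 = 21 of 48 pouches by day 14, leaving 27. The remaining 28 days at four pouches need 28 × 4 = 112, so 112 − 27 = 85 more are sent at day 14. No later resupply contact is needed.

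**3. How many patients reach 60 g/day.** The documents do not say, so the written rules were simulated (432 settings, 100,000 patients each). Assumptions: day-0 sodium uniform or skewed high on 125–132 mmol/L; 30 g adds 1–2 mmol/L to the mean rise on 15 g; between-patient SD 2 or 3.5; visit SD 1.5 or 2; values rounded to integers.

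| Assumed mean rise on 15 g (mmol/L) | Share reaching 60 g/day | Of 30 patients |
|---|---|---|
| 3 | 25–40% | 7–12 |
| 4 | 15–27% | 4–8 |
| 5 | 7–19% | 2–6 |
| 6 | 3–13% | 1–4 |
| 7 | 1–8% | 0–2 |

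**4. Sodium overshoot.** The day-14 rule sends a patient to 60 g/day only if sodium has risen by less than 6 mmol/L and is below 135. The highest such value is 134, so passing an assumed limit of 145 needs a further rise of at least 12 mmol/L. With 60 g assumed to add a mean of 2, 4 or 6 mmol/L over 30 g:

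| SD of the added rise | P(day-42 sodium above 145, given 60 g) | Expected patients in the trial, at most |
|---|---|---|
| 0 | 0–2.4% | 0.04 |
| 2 | 0–4.4% | 0.14 |
| 4 | 0.3–13.8% | 0.54 |

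Expected patients are 30 × share reaching 60 g × probability. An SD of 4 is that of the 2-day rise in the 50-patient study cited in Section 1.3.

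**5. Dose by weight.** 60/60 = 1.0 g/kg; 60/80 = 0.75; 60/100 = 0.6. The cited upper end of 0.5 g/kg is met only at 60/0.5 = 120 kg.

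**6. After the fix.** The first panel at 60 g/day falls 7 ± 2 days after the step. The time still unmeasured is 42 − 21 = 21 days, from 39 − (16 + 9) = 14 to 45 − (12 + 5) = 28.

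**The case against.** The limit is worded consistently in three places and looks deliberate: at 60 g/day there is no next dose to decide. The documents show no harm at this dose. The earlier inpatients took up to 90 g/day with no serious adverse events and no overly rapid correction. Sections 2.5.4 and 6.1.1 call the demyelination risk negligible at sodium of 125 mmol/L or more, and Section 2.3.3 says a single dose is cleared within 12 hours. Persistent symptoms halve the dose (Sections 2.3 and 10), and a cut from 60 to 30 g/day triggers a sodium check. Few patients may be affected: the rises cited in Section 1.3 are about 6–7 mmol/L, where the table gives 0–4 patients. The added panel comes with no required decision threshold and still leaves about three weeks unmeasured.

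Much of this stands. Overshoot is not a reason for the change, no rate of renal change can be claimed, and the higher counts depend on a weak response to 15 g. The cited rises come from mixed or unstated doses, so they do not settle the response to 15 g. The inpatient safety record covers a median of 4.5 days, against about 28 here. Symptom-triggered cuts do not detect a change without symptoms. A titration reason explains the wording but not the loss of the safety check, since the dose can still be reduced or stopped. The protocol already allows action on sodium and safety results, so a day-21 result could be used without a new threshold.

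**Conclusion.** The concern holds as an inexpensive patient-safety improvement, not as an error in the plan. The schedule itself is certain from the text: the 30-to-60 g/day step is the only increase without a check about a week later, and its first panel is 28 days on (23–33), at the visit where urea stops. The number affected, 0 to 12 of 30, rests on the assumed responses above. The consequence is less certain than the gap: sodium overshoot is improbable, and the documents give no rate for kidney-function change or water loss at 60 g/day.

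**What to change.** In Section 2.2 (Intervention and study period 1), strike the closing limitation so that a sodium check follows every urea dose adjustment at about 7 ± 2 days. In the day-14 visit descriptions for both periods under Research activities, strike the matching condition. The coordinator then sends every patient whose dose changes at day 14 for a basic metabolic panel in about 7 days, including those raised to 60 g/day.

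Two additions are optional in the same amendment:

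- State whether the check after a day-14 step to 30 g/day can itself lead to 60 g/day. If it can, the same one-week check should follow.
- Set a sodium value at which urea goes down one level, or stops if the patient is on 15 g/day. The sponsor would choose the value.

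The cost is one extra local blood test, and up to one call with the result, for each patient raised to 60 g/day. The instruction can be given in the call that raises the dose. IRB approval and an IND Protocol Amendment are needed, because Section 4 lists an added monitoring test as an example; this is routine for a protocol at version 13. In-person visits, endpoints, sample size and the analysis model do not change. The downside is one more laboratory trip for those patients, with 14 to 28 days still unmeasured afterwards.

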#### Follow-up research assessments:

All patients in group "Urea ON, then Urea OFF" will have scheduled follow up assessments on days 7, 14, and 42 as follows:

- Day 7: Phone interview and basic metabolic panel (BMP).
- Day 14: Phone interview and BMP. More boxes of Ure-Na will be mailed if needed to complete the study.
- Day 42: same assessment as in the baseline study visit

The phone interviews visits will focus on assessing side effects, tolerability, and adherence to urea and as appropriate, dose titration of urea. Side effects and tolerability will be assessed with questionnaires (See Medication Side Effects Questionnaire and Medication Acceptability Questionnaire). Patient also will be asked to bring their study diary to the in-person clinic visits to track their adherence to fluid restriction and urea. Visits at day 0 and day 42 will take place in the Neuromuscular Research Laboratory at the University of Pittsburgh. BMP assessment on days 7, 14 will take place at the UPMC clinical laboratory of patient's choice. At the 42-day visit, patients will be asked to return their study diary and any urea doses they did not consume. During period 1 of the study, patients randomized to group "Urea OFF, then Urea ON" will undergo same assessments as outlined for group "Urea ON, then Urea OFF", although they will not be asked about tolerability or adherence to urea as they will not be on this treatment during this period.

#### Research activities

Screening visit

• Patient will come in person to the UPMC Kidney Clinic.

- For Nephrology inpatients who meet eligibility for the study and have not started urea in the hospital, we will obtain informed consent during their hospitalization and schedule them for a screening visit within approximately 5-7 days after discharge. For Nephrology inpatients who meet eligibility for the study including a nadir serum sodium of no less than 125 mmol/L and have already started urea in the hospital, we will obtain informed consent during hospitalization, discuss with the nephrologist and/or hospitalist, we will ask them if the patient can come off urea and if so, to discontinue urea. We will then schedule these patient for a screening visit within 5-7 days after discharge. Screening visit for subjects enrolled from inpatient will take place at UPMC Kidney Clinic.
- For Nephrology outpatients who meet eligibility for the study including a nadir serum sodium of no less than 125 mmol/L and are already on urea, we will obtain informed consent, discuss with the nephrologist, we will ask them if the patient can come off urea and if so, to discontinue urea. We will then schedule these patients for a screening visit within 5-7 days after urea discontinuation. Screening visit for subjects enrolled from the outpatient setting will take place at UPMC Kidney Clinic.
- The principal investigator will obtain informed consent from the patient to be enrolled in the study.
- Patient will undergo a physical examination by principal investigator which involves: assessment of patient's ability to walk normally without help, assessment of patient's cognition with the use of the Mini-Mental State Examination test, and assessment of volume status
- The research coordinator will draw approximately 14 mL of patient's blood and send the specimen promptly to the UPMC Presbyterian clinical laboratory for processing and analysis of the following: basic metabolic panel, plasma cortisol, thyroid stimulating hormone, and plasma osmolality..
- The research coordinator will ask the patient to provide a urine sample. The research coordinator will send the specimen promptly to the UPMC Presbyterian clinical laboratory for processing and analysis of the following: urine osmolality, urine sodium, and urine pregnancy test when indicated.
- After the principal investigator analyzes the results of the physical exam and laboratory test results and determines patient eligibility for the study, the research coordinator will call the patient to inform him/her whether he/she is eligible to participate in the study.
- For patients with serum cortisol level less than 15 mcg/dL in the screening visit then we will proceed to schedule a corticotropin stimulation test (cosyntropin stimulation test) at the UPMC Montefiore Clinical and Translational Research Center.
- If patient is eligible to participate in the study then the research coordinator will give the patient instructions about the first study visit as well as mail him/her a container with instructions to collect urine for 24 hours prior to first study visit.
- If patient is not eligible to participate in the study then the principal investigator will give the patient the choice to follow up in the UPMC Kidney Clinic for the management of his/her hyponatremia.
- This visit will last approximately 1.5 hours.

First study visit (Day 0 of Period 1)

• Patient will come in person to the University of Pittsburgh Neuromuscular Research Laboratory located at [name].

- Patient will bring the container with the 24-hour urine collection he/she started the day prior. The research coordinator will send the specimen promptly to the UPMC Presbyterian clinical laboratory for processing and analysis of the following: creatinine, urea nitrogen, uric acid, osmolality, sodium, and potassium.
- The research coordinator will draw approximately 14 mL of patient's blood and send the specimen promptly to the UPMC Presbyterian clinical laboratory for processing and analysis of the following: basic metabolic panel, plasma osmolality, and plasma uric acid.
- Patient will complete SF-12 survey with pen and paper.
- A co-investigator will test patients' reactions and decision making using specialized software on a tablet computer.
- A co-investigator will test patients' balance while standing on a specialized piece of equipment. Patient will be asked to stand on both legs on top of a platform in a dynamic moving environment. Patient will go through six conditions, with three trials per condition, lasting about 20 seconds each. Patient will be asked to look forward, and stand as motionless as possible with your arms at your sides. The six conditions include the possibility of moving surroundings or moving base of support. If patient move or lose his/her balance during the procedures, patient will be asked to repeat that part again. Patient will be supported by means of a harness in the equipment to make sure he/she cannot fall over while performing the tests.
- The research coordinator will instruct the patient to restrict his/her fluid intake to no more 1200 mL/day for the next 42 ± 3 days. The research coordinator will provide the patient with a diary to record daily fluid intake.
- Patients will be randomized prior to or at the first study visit (Period 1 Day 0) following completion of baseline assessments. Our biostatistician will generate the randomization list using permuted blocks of random block sizes of 4 and 6 and our systems analyst will load the list into RedCAP. To preserve allocation concealment for consecutively enrolled participants, we will use the randomization module in RedCAP to assign each participant 1:1 to either On-to-Off Urea sequence or Off-to-On Urea sequence.
- If patient is randomized to take On-to-Off Urea sequence then the research coordinator will give the patient 48 urea powder pouches with instructions on how to take the urea every day. The research coordinator will provide the patient with a diary to record patient's daily urea intake.
- This visit will last approximately 2.5 hours.

Second study visit (Day 7 of Period 1)

- The research coordinator will call the patient on the phone to ask some questions about any new symptoms patient might have experienced since his/her last visit.
- The research coordinator will direct the patient to go the UPMC clinical laboratory of the patient's choice that day to have his blood drawn for analysis of a basic metabolic panel.
- If patient is taking urea, we might call the participant on the phone again to ask to change the dose of urea depending on the sodium level results.
- This visit will last approximately 20 minutes.

Third study visit (Day 14 of Period 1)

- The research coordinator will call the patient on the phone to ask some questions about any new symptoms patient might have experienced since his/her last visit.
- The research coordinator will direct the patient to go the UPMC clinical laboratory of the patient's choice that day to have his blood drawn for analysis of a basic metabolic panel.
- The research coordinator will instruct the patient to bring his fluid and urea intake diaries to the next study visit.
- The research coordinator will give or mail the patient a container with instructions to collect urine for 24 hours prior to next study visit.
- If patient is taking urea then research coordinator will give and/or mail the patient enough urea powder pouches to complete his/her participation in this period of the study.
- If patient is taking urea, we might call the participant on the phone to ask to change the dose of urea depending on the sodium level results.
- If urea dose is adjusted to less than the maximum allowed dose, research coordinator will direct the patient to go the UPMC clinical laboratory of the patient's choice in approximately 7 days to have his/her blood drawn for analysis of a basic metabolic panel.
- This visit will last approximately 30 minutes.

Reminder telephone call

• The research coordinator will call the patient on the phone 48-72 hours before the next study visit to remind him/her of the upcoming study visit.

Fourth study visit (Day 42 of Period 1)

- Patient will come in person to the University of Pittsburgh Neuromuscular Research Laboratory located at [name].
- The research coordinator will collect the patient's fluid and urea intake diaries.
- The research coordinator will ask the patient some questions about any new symptoms patient might have experienced since his/her last visit.
- If patient is taking urea then the research coordinator will ask patient some questions related to acceptability of urea.
- Patient will bring the container with the 24-hour urine collection he/she started the day prior. The research coordinator will send the specimen promptly to the UPMC Presbyterian clinical laboratory for processing and analysis of the following: creatinine, urea nitrogen, uric acid, osmolality, sodium, and potassium
- The research coordinator will draw approximately 14 mL of patient's blood and send the specimen promptly to the UPMC Presbyterian clinical laboratory for processing and analysis of the following: basic metabolic panel, plasma osmolality, and plasma uric acid.
- Patient will complete the SF-12 survey with pen and paper.
- A co-investigator will test patients' reactions and decision making using specialized software on a tablet computer.
- A co-investigator will test patients' balance while standing on a specialized piece of equipment. Patient will be asked to stand on both legs on top of a platform in a dynamic moving environment. Patient will go through six conditions, with three trials per condition, lasting about 20 seconds each. Patient will be asked to look forward, and stand as motionless as possible with your arms at your sides. The six conditions

include the possibility of moving surroundings or moving base of support. If patient move or lose his/her balance during the procedures, patient will be asked to repeat that part again. Patient will be supported by means of a harness in the equipment to make sure he/she cannot fall over while performing the tests.

- The research coordinator will ask patient to stop fluid restriction.
- If patient is taking urea then the research coordinator will instruct the patient to stop taking urea and return all the urea pouches he/she did not use to the research coordinator.
- The research coordinator will provide the patient with a container with instructions to collect urine for 24 hours prior to next study visit.
- This visit will last approximately 2.5 hours.

Reminder telephone call

• The research coordinator will call the patient on the phone 48-72 hours before the next study visit to remind him/her of the upcoming study visit.

Fifth study visit (Day 0 of Period 2)

- Patient will come in person to the University of Pittsburgh Neuromuscular Research Laboratory located at [name].
- Patient will bring the container with the 24-hour urine collection he/she started the day prior. The research coordinator will send the specimen promptly to the UPMC Presbyterian clinical laboratory for processing and analysis of the following: creatinine, urea nitrogen, uric acid, osmolality, sodium, and potassium.
- The research coordinator will draw approximately 14 mL of patient's blood and send the specimen promptly to the UPMC Presbyterian clinical laboratory for processing and analysis of the following: basic metabolic panel, plasma osmolality, and plasma uric acid.
- Patient will be given the SF-12 survey to complete with pen and paper.
- A co-investigator will test patients' reactions and decision making using specialized software on a tablet computer.
- A co-investigator will test patients' balance while standing on a specialized piece of equipment. Patient will be asked to stand on both legs on top of a platform in a dynamic moving environment. Patient will go through six conditions, with three trials per condition, lasting about 20 seconds each. Patient will be asked to look forward, and stand as motionless as possible with your arms at your sides. The six conditions include the possibility of moving surroundings or moving base of support. If patient move or lose his/her balance during the procedures, patient will be asked to repeat that part again. Patient will be supported by means of a harness in the equipment to make sure he/she cannot fall over while performing the tests.
- The research coordinator will instruct the patient again to restrict his/her fluid intake to no more 1200 mL/day for the next 42 ± 3 days. The research coordinator will provide the patient with a new diary to record daily fluid intake.
- If patient was randomized to take Off-to-On Urea sequence then the research coordinator will give the patient 48 urea powder pouches with instructions on how to take the urea every day. The research coordinator will provide the patient with a new diary to record patient's daily urea intake.
- This visit will last approximately 2.5 hours.

Sixth study visit (Day 7 of Period 2)

- The research coordinator will call the patient on the phone to ask some questions about any new symptoms patient might have experienced since his/her last visit.
- The research coordinator will direct the patient to go the UPMC clinical laboratory of the patient's choice that day to have his/her blood drawn for analysis of a basic metabolic panel.
- If patient is taking urea, we might call the participant on the phone again to ask to change the dose of urea depending on the sodium level results.
- This visit will last approximately 20 min.

Seventh study visit (Day 14 of Period 2)

- The research coordinator will call the patient on the phone to ask some questions about any new symptoms patient might have experienced since his/her last visit.
- The research coordinator will direct the patient to go the UPMC clinical laboratory of the patient's choice that day to have his blood drawn for analysis of a basic metabolic panel.
- The research coordinator will instruct the patient to bring his fluid and urea intake diaries to the next study visit.
- The research coordinator will give or mail the patient a container with instructions to collect urine for 24 hours prior to next study visit.
- If patient is taking urea then research coordinator will give and/or mail the patient enough urea powder pouches to complete his/her participation in this period of the study.
- If patient is taking urea, we might call the participant on the phone to ask to change the dose of urea depending on the sodium level results.
- If urea dose is adjusted to less than the maximum allowed dose, research coordinator will direct the patient to go the UPMC clinical laboratory of the patient's choice in approximately 7 days to have his/her blood drawn for analysis of a basic metabolic panel.
- This visit will last approximately 30 minutes.

Reminder telephone call

• The research coordinator will call the patient on the phone 48-72 hours before the next study visit to remind him/her of the upcoming study visit.

Eighth study visit (Day 42 of Period 2)

- Patient will come in person to the University of Pittsburgh Neuromuscular Research Laboratory located at [name].
- The research coordinator will collect the patient's fluid and urea intake diaries.
- The research coordinator will ask the patient some questions about any new symptoms patient might have experienced since his/her last visit.
- If patient is taking urea then the research coordinator will ask patient some questions related to acceptability of urea.
- Patient will bring the container with the 24-hour urine collection he/she started the day prior. The research coordinator will send the specimen promptly to the UPMC

Presbyterian clinical laboratory for processing and analysis of the following: creatinine, urea nitrogen, uric acid, osmolality, sodium, and potassium.

- The research coordinator will draw approximately 14 mL of patient's blood and send the specimen promptly to the UPMC Presbyterian clinical laboratory for processing and analysis of the following: basic metabolic panel, plasma osmolality, and plasma uric acid.
- Patient will be given the SF-12 survey to complete with pen and paper.
- A co-investigator will test patients' reactions and decision making using specialized software on a tablet computer.
- A co-investigator will test patients' balance while standing on a specialized piece of equipment. Patient will be asked to stand on both legs on top of a platform in a dynamic moving environment. Patient will go through six conditions, with three trials per condition, lasting about 20 seconds each. Patient will be asked to look forward, and stand as motionless as possible with your arms at your sides. The six conditions include the possibility of moving surroundings or moving base of support. If patient move or lose his/her balance during the procedures, patient will be asked to repeat that part again. Patient will be supported by means of a harness in the equipment to make sure he/she cannot fall over while performing the tests.
- The research coordinator will instruct patient to stop fluid restriction.
- If patient is taking urea then the research coordinator will instruct the patient to stop taking urea and return all the urea pouches he/she did not use to the research coordinator.
- The principal investigator will give the patient the choice to follow up in the UPMC Kidney Clinic to continue the management of his/her hyponatremia.
- This visit will last approximately 2.5 hours.

